8.2 Safety Assessments

Planned time points for all safety assessments are provided in the SoA (Section 1.3).

8.2.1 Physical Examinations

Physical examinations, with weight, will be performed regularly at Day 1 of every cycle, at the end of treatment and during the safety follow-up visits, as indicated in the SoA (Section 1.3). Height will be recorded at screening only.

A complete physical examination will be performed and include assessments of the following: general appearance, respiratory, cardiovascular, abdomen, skin, head and neck (including ears, eyes, nose, and throat), lymph nodes, thyroid, musculoskeletal (including spine and extremities), urogenital, dermatological, gastrointestinal, endocrine, haematologic/lymphatic, neurological systems, height, and weight. Targeted physical examinations are to be used by the investigator on the basis of clinical observations and symptomatology.

Physical examination, as well as assessment of height and weight, will be performed at timelines as specified in the SoA.

Investigators should pay special attention to clinical signs related to previous serious illnesses, new or worsening abnormalities may qualify as AEs; see Section 8.3.5 for details.

8.2.2 Vital Signs

Vital signs (body temperature, BP, respiratory rate, and heart [pulse] rate) will be performed at timelines as specified in the SoA. Any changes in vital signs should be recorded as an AE if applicable.

For patients taking ceralasertib monotherapy: Blood pressure and pulse measurements will be assessed with a completely automated device. Manual techniques will be used only if an automated device is not available.

Blood pressure and pulse measurements should be preceded by at least 5 minutes of rest for the patient in a quiet setting without distractions (eg, television, cell phones).

Vital signs (to be taken before blood collection for laboratory tests) will consist of 1 pulse and 3 blood pressure measurements (3 consecutive blood pressure readings will be recorded at intervals of at least 1 minute). The average of the 3 blood pressure readings will be recorded on the eCRF.

Situations in which vital signs results should be reported as AEs are described in Section 8.3.5.

For patients receiving ceralasertib plus durvalumab: On the first infusion day (Day 8 of each treatment cycle except for the patients in the ceralasertib monotherapy arm in the main study), patients in the ceralasertib plus durvalumab arm will be monitored and vital signs collected/recorded in the eCRF prior to, during, and after infusion of study treatment as presented in the bulleted list below.

Blood pressure and pulse will be collected from patients in the IO arms before, during, and after each infusion at the following times (based on a 60-minute infusion):

- Prior to the beginning of the infusion (measured once from approximately 30 minutes before up to 0 minutes [ie, the beginning of the infusion])
- Approximately 30 minutes during the infusion (halfway through infusion)
- At the end of the infusion (approximately 60 minutes \pm 5 minutes)

If the infusion takes longer than 60 minutes, then blood pressure and pulse measurements should follow the principles as described above or be taken more frequently if clinically indicated. A 1-hour observation period is recommended after the first infusion of durvalumab.

Vital signs at subsequent infusions (ceralasertib plus durvalumab)

Blood pressure, pulse and other vital signs should be measured, collected/recorded in eCRF prior to the start of the infusion. Patients should be carefully monitored and blood pressure and other vital signs should be measured during and post infusion as per institution standard and as clinically indicated. Any clinically significant changes in vital signs should be entered onto an unscheduled vital signs CRF page. If no infusion reaction has occurred with the initial infusion, and at the discretion of the investigator, the 1-hour observation period may be shortened or eliminated.

8.2.3 Electrocardiograms

An electrocardiogram will be performed at timepoints as specified in the SoA (Section 1.3).

Resting 12-lead ECG

Triplicate 12-lead ECGs will be done at screening, and single ECG readings will be collected at other visits as clinically indicated. The patient should rest in a semi-supine position for at least 5 minutes before and also during the recording. The ECG machine will automatically calculate the heart rate and measures PR, QRS, QT, and QTcF intervals.

All ECGs should be assessed by the investigator as to whether they are clinically significantly abnormal. Any clinically significant abnormalities detected including a QTcF value > 470 ms require triplicate ECG results. For triplicate ECGs, 3 individual ECG tracings should be obtained in succession, no more than 2 minutes apart. The full set of triplicates should be completed within 5 minutes (5 to 15 minutes window period).

8.2.4 Eastern Cooperative Oncology Group Performance Status

Performance status will be assessed at the visits indicated in the SoA, according to ECOG criteria as follows:

 Table 13
 Eastern Cooperative Oncology Group Performance Status

Grade	Eastern Cooperative Oncology Group
0	Fully active, able to carry out all pre-disease activities without restrictions
1	Restricted in strenuous activity but ambulatory and able to carry out work of a light or sedentary nature eg, light housework, office work
2	Ambulatory and capable of self-care, but unable to carry out any work activities. Up and about more than 50% of waking hours
3	Capable of only limited self-care, confined to bed or chair more than 50% of waking hours
4	Completely disabled, cannot carry out self-care, totally confined to bed or chair
5	Dead

Any significant change from baseline or screening in the ECOG performance status must be reported as an AE.

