Procedure	Screening a			Inte	rvention	period ((28-day	cycles)				Post-in	tervent	ion follo	ow-up peri	od	Details in CSP section or appendix
	Scr		Cycl	es 1-2			Cycle 3	3	C4-on	wards	ntinued tment)	(# (follow- after las	_	al ftil W)	
Cycle Day	-21 to -1	Day 1	Day 7	Day 8	Day 15	Day 1	Day 7	Day 8	Day 1	Day 8	Study Treatment Discontinued (last dose of study treatment)	30 days	60 days	90 days	180 days (6 months)	Progression/Survival Follow-up (Q8W until 18 months, then Q12W)	
Visit window (± days)	-	-	-	-	± 1	± 3	-	± 1	± 3	± 1	Study Ti	± 3	± 7	± 7	±7	Prog Follo 18 mc	
ECOG performance status ¹	X	X		X		X		X	X		X	X	X	X	X	X	Section 8.2.4
Hepatitis B and C and HIV screening	X																Sections 5.1 and 8.2.5
Safety laboratory assessments (clinical chemistry including TSH, haematology, urinalysis ^{f, k, m})	X	X		X	X	X		X	X	X	X	X	Х	X			Section 8.2.5
Coagulation parameters ⁿ	X									X							Section 8.2.5
Pregnancy test (WOCBP only)°	X	X				X			X			X	X	X			Section 8.2.5
AE	X		+		t every v		nay be	X conducte	d by pho		tied to a vis		\rightarrow				Section 8.3
Concomitant medications	X		+		t every v		nay be	X conducte	d by pho	== ne if not	tied to a vis		\rightarrow				Section 6.5

Procedure	Screening a			Inte	rvention	period ((28-day	cycles)				iod	Details in CSP section or appendix				
	Scr		Cycl	es 1-2			Cycle 3	3	C4-on	wards	ntinued tment)	(#		ty follow-up s after last dose)		al frii W)	
Cycle Day	-21 to -1	Day 1	Day 7	Day 8	Day 15	Day 1	Day 7	Day 8	Day 1	Day 8	Study Treatment Discontinued (last dose of study treatment)	30 days	60 days	90 days	180 days (6 months)	Progression/Survival Follow-up (Q8W until 18 months, then Q12W)	
Visit window (± days)	-	-	-	-	± 1	± 3	-	± 1	± 3	±1	Study T	± 3	±7	± 7	± 7	Proj Folk 18 me	
Tumour imaging (RECIST 1.1; CT/MRI including brain scan at baseline) p, s	Xq					Tumour assessments will be conducted every 8 weeks (±1 week) after start of treatment (C1D1) up to 18 months, then every 12 weeks (±1 week) until objective disease progression per RECIST 1.1. If a patient discontinues without disease progression, RECIST tumour assessments will be performed every 8 weeks for 18 months, then every 12 weeks, thereafter.										Section 8.1.1	
CCI																	

Procedure	Screening a			Inte	rvention	period ((28-day	cycles)				Post-in	tervent	ion follo	w-up peri	od	Details in CSP section or appendix
	Sere		Cycl	es 1-2			Cycle 3		C4-on	wards	ntinued tment)	(# (/ follow- after las		al rtil W)	

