 Ceralasertib Monotherapy (Main Study)

D I	Screening a		I	ntervent	tion per	riod (28	-day cyc	cles)		Pos	st-intervention follo	Details in CSP section or appendix	
Procedure	Scree	(Cycles 1	1-2	Cycle 3			C4-onwards		t itment)	Safety follow-up	Progression/Survival Follow-up	
Cycle Day	-21 to -1	Day 1	Day 7	Day 15	Day 1	Day 7	Day 15	Day 1	Day 15	Study Treatment Discontinued (Last dose of study treatment)	30 days after last dose	(Q8W until 18 months, then Q12W)	
Visit window (± days)	-	-	-	± 1	± 3	-	± 1	± 3	± 1	(Last	± 3	± 7	
Informed consent: main study ^b	X												Section 5 and Appendix A 3
Informed consent: genetic sample and analysis (optional) ^b	X												Section 5.1 and Appendix A 3
Archival tumour sample, mandatory ^c	X												Section 8.6.1
Fresh tumour biopsy	X			X (C2 only)						X (PD)			Section 8.6.1
Inclusion and exclusion criteria e, f	X	X											Sections 5.1, 5.2 and 5.4
Demography ^g	X												Section 5.1
Prior anti-cancer therapy h	X												Section 5.1
Full physical examination ^a	X	X			X			X		X	X		Section 8.2.1
Targeted physical examination ⁱ			X	X		X	X		X				Section 8.2.1

D	Screening a		I	ntervent	tion per	riod (28	-day cyc	cles)		Pos	Details in CSP section or appendix		
Procedure	Scree	(Cycles 1	l-2		Cycle			t itment)	Safety follow-up	Progression/Survival Follow-up		
Cycle Day	-21 to -1	Day 1	Day 7	Day 15	Day 1	Day 7	Day 15	Day 1	Day 15	Study Treatment Discontinued (Last dose of study treatment)	30 days after last dose	(Q8W until 18 months, then Q12W)	
Visit window (± days)	-	-	-	± 1	± 3	-	± 1	± 3	± 1	(Last	± 3	± 7	
Height	X												Section 8.2.1
Weight a	X	X		X	X		X	X	X	X	X		Section 8.2.1
Past and current medical conditions	X	X a											Sections 5.1 and 5.2
12-lead ECG ^{j, k}	X (Trip licat e)			As clinic	ally ind	icated;	single E0	CGs					Section 8.2.3
Echocardiogram/MU GA	X			As	s clinica	ılly indi	cated			X			Section 8.2.6.1
Vital signs k	X	X	X	X	X	X	X	X	X	X	X		Section 8.2.2
ECOG performance status ¹	X	X			X			X		X			Section 8.2.4
Hepatitis B and C and HIV screening	X												Section 5.1 and 8.2.5
Safety laboratory assessments (clinical chemistry including TSH, haematology, urinalysis) ^{f, k, m}	X	X	X	X	X	X	X	Х	X	Х	X		Section 8.2.5

Procedure	Screening a		I	ntervent	tion per	riod (28	3-day cyc	cles)		Pos	t-intervention follo	Details in CSP section or appendix		
	Scree	(Cycles 1	1-2	Cycle 3			C4-onwards		t itment)	Safety follow-up	Progression/Surviva Follow-up		

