- Clinical laboratory assessment parameters are to be assessed at baseline on Day 1 (unless all screening laboratory assessments are performed within 3 days prior to Day 1) and full blood count result should be checked prior to dosing when assessed on a dosing day. Serum or plasma clinical chemistry (including LFT monitoring) and haematology may be performed more frequently if clinically indicated. Urinalysis should be performed at baseline (screening) and then as clinically indicated. Thyroid stimulating hormone testing is to be done at the timepoints indicated and also when clinically indicated (clinically suspecting immune-related hypo/hyper thyroidism). Free T3 or free T4 will only be measured if TSH is abnormal or if there is clinical suspicion of an AE related to the endocrine system.
- Baseline demographics will include all prior treatments (start/stop dates, best response, treatment line, reason for treatment discontinuation and, if due to RECIST 1.1-defined disease progression, how progression was determined and dates of radiographic scans indicating disease progression per RECIST 1.1) and disease stage at diagnosis and at study entry. Other genomic characteristics will be collected where known eg, NRAS, c-kit, PD-(L)1, NF1, MSI.
- Collect prior anti-cancer therapies, including best response, setting (eg, adjuvant/metastatic), prior radiotherapy, and prior surgery. For the prior anti-PD-(L)1 regimen, also collect reason for discontinuation and details of scans indicating RECIST 1.1 disease progression, including anonymised copies of the scan reports.
- ¹ Additional physical examination will be performed, if clinically indicated.
- Triplicate ECGs at screening only. Subsequent ECGs should only be taken if clinically indicated.
- Whenever ECG, vital signs and blood draws are scheduled on the same day, it is recommended that the assessments occur in the following order: vital signs, ECG, and then blood draws. The timing of the ECG and vital signs assessments must allow for the blood draw (eg, PK blood sample) to occur at the scheduled time points.
- ECOG assessment also to be performed at initiation of subsequent anticancer therapy, where possible. In addition, ECOG performance status should be collected at initiation of subsequent anticancer therapy, if appropriate site staff are available to collect such information. Additional ECOG assessments may be performed (eg, on Day 15), if clinically indicated.

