8.3.1 Time Period and Frequency for Collecting AE and SAE Information

Adverse events and SAEs will be collected from time of signature of ICF, throughout the treatment period and including the safety follow-up period (30 days after last dose of study treatment for ceralasertib monotherapy or 90 days after last dose of study treatment for ceralasertib and durvalumab combination).

If the investigator becomes aware of an SAE with a suspected causal relationship to the study treatment that occurs after the end of the clinical study in a patient treated by him or her, the investigator shall, without undue delay, report the SAE to the sponsor as described in Section 8.3.12.

For patients continuing in the PTAP, AEs and SAEs will be recorded by the treating physician from the time the participant signs informed consent and will continue throughout the program until the end of the PTAP or until consent has been withdrawn. Collection and reporting of AEs and SAEs after the final DCO is described in Section 8.3.11.

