9.4.3 Safety

All safety analyses will be performed on the safety analysis set. Safety and tolerability will be assessed in terms of AEs (including SAEs), deaths, laboratory data, vital signs, and ECOG. These will be collected for all patients. Appropriate summaries of these data will be presented.

In general, the baseline values for statistical analysis is the last non-missing value prior to administration of the first dose of study treatment. Details are described in the SAP.

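### ECOG is scheduled more often in the combination arm in Cycles 1-3 and at the 30-day visit, and significant ECOG changes must be reported as AEs, so ECOG summaries and ECOG-triggered AEs can be inflated in that arm

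*Protocol*

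**What the plan says.** Protocol Section 8.2.4 takes the timing of ECOG from the schedule of activities: "Performance status will be assessed at the visits indicated in the SoA, according to ECOG criteria as follows". It then sets a reporting rule for all patients: "Any significant change from baseline or screening in the ECOG performance status must be reported as an AE". It does not define what makes a change significant.

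Section 9.4.3 counts ECOG among the safety variables: "Safety and tolerability will be assessed in terms of AEs (including SAEs), deaths, laboratory data, vital signs, and ECOG". Section 9.4.3.1 tabulates AEs by treatment arm, and the summary tables hold only treatment-emergent events. The window for these closes 30 days after last dose, or at the start of subsequent cancer therapy if that is earlier. Later AEs are listed only.

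Section 1.3 schedules the row "ECOG performance status" differently in the two main-study arms:

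| Timepoint | Table 1, combination | Table 2, monotherapy |
|---|---|---|
| Screening | yes | yes |
| Cycles 1-3, Day 1 | yes | yes |
| Cycles 1-3, Day 8 | yes | no such visit; Day 7 and Day 15 visits have no ECOG |
| Cycle 4 onward, Day 1 | yes | yes |
| Discontinuation | yes | yes |
| 30 days after last dose | yes | visit takes place, no ECOG |
| 60, 90, 180 days | yes | no such visits |
| Progression/survival follow-up | yes | no |

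A footnote common to both tables adds: "Additional ECOG assessments may be performed (eg, on Day 15), if clinically indicated".

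**The concern.** A mandatory AE rule is attached to a measurement whose frequency depends on the arm. The more often a patient is rated, the more chances there are for a significant change to be seen and entered as an AE, and the worse the worst recorded grade is likely to be. This happens even if the true course is the same in both arms.

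The timing adds to this. Both arms take ceralasertib on Days 1-7, and Section 2.3.1.1 names fatigue/asthenia as an identified ceralasertib risk. The combination arm is rated on Day 8, the first day off ceralasertib. The next scheduled monotherapy rating is Day 1 of the following cycle, 21 days later. Section 4.2 says the monotherapy arm is there to show what ceralasertib contributes to the combination. A short-lived ceralasertib effect recorded in one arm only could be read as a cost of adding durvalumab, and nothing in a side-by-side table would reveal the cause.

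**Working it through.** The protocol gives no figure on this point to reproduce. The check is a count of scheduled readings, followed by an illustration.

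**Scheduled readings (Section 1.3, Tables 1 and 2)**

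- Cycles 1-3, combination: 2 days x 3 cycles = 6. Monotherapy: 1 day x 3 cycles = 3.
- Without the Cycle 1 Day 1 baseline: 6 - 1 = 5 against 3 - 1 = 2.
- Cycle 4 onward: 1 per cycle in each arm.
- Discontinuation: 1 in each arm.
- Safety visits after last dose: 4 (30, 60, 90 and 180 days) against 0.

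**Which post-treatment readings can reach the by-arm AE summaries**

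- Section 9.4.3.1 closes the summary window at 30 days, so changes first seen at 60, 90 or 180 days are listed only.
- Section 8.3.1 collects AEs for "30 days after last dose of study treatment for ceralasertib monotherapy or 90 days after last dose of study treatment for ceralasertib and durvalumab combination", so the 180-day reading also falls outside routine AE collection.
- That leaves the 30-day visit: 1 against 0. Its window is ±3 days, so some of those readings also fall after Day 30.
- Section 9.4.3 sets no such window for the ECOG summary itself. A worst-value summary could therefore still take in the later combination readings.

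**Illustration (assumption, not from the protocol)**

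Suppose a decline lasts d days and its onset is uniform over a 28-day cycle. The chance that at least one scheduled reading falls within it is:

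- Day 1 only (monotherapy): min(d, 28)/28
- Day 1 and Day 8 (combination): [min(d, 7) + min(d, 21)]/28. The two terms are the 7-day gap from Day 1 to Day 8 and the 21-day gap from Day 8 to the next Day 1.

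| d (days) | Combination | Monotherapy |
|---|---|---|
| 3 | (3+3)/28 = 21% | 3/28 = 11% |
| 7 | (7+7)/28 = 50% | 7/28 = 25% |
| 14 | (7+14)/28 = 75% | 14/28 = 50% |
| 21 | (7+21)/28 = 100% | 21/28 = 75% |
| 28 | (7+21)/28 = 100% | 28/28 = 100% |

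Under this assumption the gap concerns transient declines and is gone at 28 days. The differences are upper bounds, because scheduled ECOG is not the only route by which a decline becomes an AE.

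**The case against.** The strongest reply is that monotherapy patients are not unobserved between Day 1 visits. In Cycles 1-3 they attend on Day 7 and Day 15, with a targeted physical examination and vital signs each time. AEs are collected throughout in both arms by an open question and by observation (Section 8.3.4), and clinically relevant new examination findings are AEs (Section 8.3.5). Unscheduled ECOG is allowed in both arms. Examinations in Cycles 1-3 number 9 in monotherapy (3 full, 6 targeted) against 8 in the combination (3 full, 5 targeted). Safety laboratory visits are also 9 against 8. Decline unequivocally due to progression is not an AE (Section 8.3.7). Patients are counted once per preferred term, so a patient already recorded with fatigue adds nothing under that term. Safety is descriptive, and ECOG is not among the safety endpoints in Table 5.

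All of this stands, and it rules out two stronger readings. A reader might infer that the whole between-arm harm comparison is biased against the combination. The documents do not support that, because other scheduled checks in Cycles 1-3 are no heavier in that arm. A reader might also compute how many Day 8 declines have gone by the next Day 1. With exponential durations of mean 7, 14 or 28 days, exp(-21/mean) gives 5%, 22% or 47% persisting, hence 53% to 95% missed in monotherapy. Those durations are not in the protocol, and the calculation treats scheduled ECOG as the only way a decline can be found.

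The reply does not remove the asymmetry. Open questioning and optional ratings do not equal a scheduled rating with a mandatory reporting rule. Infusion safety does not readily explain the Day 8 reading either: durvalumab is still given on Day 8 from Cycle 4, where Table 1 has no Day 8 ECOG, and Table 3 gives the same combination with on-treatment ECOG on Day 1 only. Table layout can be left to the SAP, but the unequal schedule and the AE rule are both fixed in the protocol.

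**Conclusion.** The concern holds in a limited form. Scheduled ECOG ascertainment is unequal: 6 against 3 readings in Cycles 1-3 (5 against 2 after baseline) and 1 against 0 at the 30-day visit. Combined with the AE rule in Section 8.2.4, this can inflate ECOG summaries and ECOG-triggered AEs in the combination arm, for transient declines in Cycles 1-3 and for changes first seen at 30 days.

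It does not extend to scheduled on-treatment ECOG from Cycle 4 Day 1, to discontinuation, to by-arm AE summaries after 30 days, or to harms found by other routes. The direction follows from the schedule. The size does not: the protocol gives no rate of AEs that arise only from an ECOG reading, no duration of decline, and no threshold for a significant change. The detection percentages above rest on an assumed uniform onset and serve only as an illustration.

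**What to change.** 1. In Section 9.4.3, base the between-arm ECOG shift and worst-value summary on timepoints common to both arms: Day 1 of each cycle and discontinuation. List Day 8 and post-treatment readings separately.
2. Flag AEs whose only source is a Day 8 or follow-up ECOG reading, and show the by-arm AE summary with and without them.
3. For monotherapy patients still on treatment, add ECOG to the existing 30-day safety visit in Table 2.

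Adding ECOG to the monotherapy Day 7 visit is not worthwhile. The summary of changes says recruitment has ended, Table 2 has no Day 7 visit from Cycle 4, and the combination arm has no Day 8 ECOG from Cycle 4.

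The cost is some analysis wording, one AE flag, and one rating at a visit that already takes place. The downside is that some ECOG records leave the comparative table. Early-cycle monotherapy readings that were never taken cannot be recovered, so for Cycles 1-3 the remedy is analytic only.

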8.3.5 Adverse Events Based on Examinations and Tests

The results from the protocol mandated laboratory tests, vital signs, physical examinations, ECGs, and echocardiograms/MUGA scans will be summarised in the CSR.

Deterioration as compared to baseline in protocol-mandated laboratory values and vital signs should therefore only be reported as AEs if they fulfil any of the SAE criteria, are the reason for discontinuation of treatment with the study treatment or are considered to be clinically relevant as judged by the investigator (which may include but not limited to consideration as to whether treatment or non-planned visits were required or other action was taken with the study treatment, eg, dose adjustment or study treatment interruption).

If deterioration in a laboratory value/vital sign/physical examination/ECG/echocardiogram/MUGA is associated with clinical signs and symptoms, the sign or symptom will be reported as an AE and the associated laboratory result/vital sign/physical examination/ECG/echocardiogram/MUGA will be considered as additional information. Wherever possible the reporting investigator uses the clinical, rather than the laboratory term (eg, anaemia versus low haemoglobin value). In the absence of clinical signs

or symptoms, clinically relevant deteriorations in non-mandated parameters should be reported as AE(s).

Deterioration of a laboratory value, which is unequivocally due to disease progression per RECIST 1.1, should not be reported as an AE/SAE.

Any new or aggravated clinically relevant abnormal medical finding at a physical examination as compared with the baseline assessment will be reported as an AE unless unequivocally related to the disease under study.

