8.3.7 Disease Progression

Disease progression can be considered as a worsening of a patient's condition attributable to the disease for which the study treatment is being evaluated. It may be an increase in the severity of the disease under study and/or increases in the symptoms of the disease. The development of new, or progression of existing metastasis to the primary cancer under study should be considered as disease progression and not an AE. Events, which are unequivocally due to disease progression, should not be reported as an AE during the study. If the disease progression worsens in terms of time-course or severity compared to what would normally be expected for that patient, or if the investigator considers that there was a causal relationship between treatment with the study medication(s) or protocol procedures and the disease progression, the event must be reported as an SAE/SUSAR.

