9.4.3.1 Adverse Events

AEs will be listed individually by patient and treatment group. For patients who undergo a dose modification, all AEs (due to drug or otherwise) will be assigned to the initial dose group.

Medical Dictionary for Regulatory Activities will be used to code AEs. Adverse events will be graded according to the National Cancer Institute CTCAE (Version 5.0). The number of patients in each treatment arm experiencing each AE will be summarised by MedDRA system organ class and preferred term. The number and percentage of patients with AEs in different categories (eg, causally related, CTCAE Grade \geq 3, etc) will be summarised by treatment arm; events in each category will be further summarised by MedDRA system organ class and preferred term. Serious adverse events will be summarised separately, if a sufficient number occurs.

Adverse event summary tables will include only treatment-emergent AEs. Adverse Events will be defined as treatment-emergent if they onset or worsen (by investigator report of a change in intensity), during the study treatment or safety follow-up period (defined as 30 days after last dose of study treatment) but prior to subsequent cancer therapy. AEs outside this period will only be listed.

During the evaluation of the AE data, an AstraZeneca medically qualified expert will review the list of AEs that were not reported as SAEs and AEs leading to discontinuation. Based on the expert's judgement, significant AEs of particular clinical importance may, after consultation with the Global Patient Safety Physician, be considered OAEs and reported as such in the clinical study report. A similar review of laboratory/vital signs (pulse and blood pressure) will be performed for identification of OAEs. Examples of these could be marked haematological and other laboratory abnormalities, and certain events that lead to treatment (other than those already classified as serious), dose reduction, or significant additional treatment.

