An adverse event is the development of any untoward medical occurrence (other than progression of the malignancy under evaluation) in a patient or clinical study patient administered a study treatment and which does not necessarily have a causal relationship with this treatment. An AE can therefore be any unfavourable and unintended sign (eg, an abnormal laboratory finding), symptom (for example nausea, chest pain), or disease temporally associated with the use of a medicinal product, whether or not considered related to the medicinal product.

The term AE is used to include both serious and non-serious AEs and can include a deterioration of a pre-existing medical occurrence. An AE may occur at any time, including run-in or washout periods, even if no study treatment has been administered.

B 2 Definitions of Serious Adverse Event

An SAE is an AE occurring during any study phase (ie, run-in, treatment, washout, follow-up), that fulfils one or more of the following criteria:

- Results in death
- Is immediately life-threatening
- Requires in-patient hospitalisation or prolongation of existing hospitalisation
- Results in persistent or significant disability or incapacity
- Is a congenital abnormality or birth defect
- Is an important medical event that may jeopardise the patient or may require medical treatment to prevent one of the outcomes listed above

Adverse Events (AEs) for **malignant tumours** reported during a study should generally be assessed as **Serious AEs**. If no other seriousness criteria apply, the 'Important Medical Event' criterion should be used. In certain situations, however, medical judgement on an individual event basis should be applied to clarify that the malignant tumour event should be assessed and reported as a **non-serious AE**. For example, if the tumour is included as medical history and progression occurs during the study, but the progression does not change treatment and/or prognosis of the malignant tumour, the AE may not fulfil the attributes for being assessed as serious, although reporting of the progression of the malignant tumour as an AE is valid and should occur. Also, some types of malignant tumours, which do not spread remotely after a routine treatment that does not require hospitalisation, may be assessed as non-serious;

examples in adults include Stage 1 basal cell carcinoma and Stage 1A1 cervical cancer removed via cone biopsy.

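### Section 8.2.4 makes every significant ECOG change a mandatory AE, without the disease-progression exception in 8.3.5, 8.3.7 and Appendix B 1, so AE counts depend on which section a site follows

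*Protocol*

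**What the plan says.** Section 8.2.4, after the ECOG grade table, sets an unconditional rule: "Any significant change from baseline or screening in the ECOG performance status must be reported as an AE". It does not define a significant change and points to no other section.

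Three other places treat progression differently:

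- Section 8.3.7 (Disease Progression): "Events, which are unequivocally due to disease progression, should not be reported as an AE during the study". Its description of progression is broad: "It may be an increase in the severity of the disease under study and/or increases in the symptoms of the disease".
- Appendix B 1 (Definition of Adverse Events) covers "any untoward medical occurrence (other than progression of the malignancy under evaluation", with the exclusion in parentheses.
- Section 8.3.5 says that a new or worsened clinically relevant finding at physical examination "will be reported as an AE unless unequivocally related to the disease under study". It has a similar carve-out for laboratory values and does not mention ECOG.

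On the analysis side, Section 9.4.3.1 says: "Adverse event summary tables will include only treatment-emergent AEs". Emergence is defined by onset or worsening "during the study treatment or safety follow-up period (defined as 30 days after last dose of study treatment) but prior to subsequent cancer therapy". The protocol states no filter for events due to progression.

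**The concern.** A decline in performance status caused by advancing melanoma is a common form of symptomatic progression. Under 8.2.4 it has to be reported as an AE; under 8.3.7 and the AE definition it should not be. No order of precedence is stated, so two sites could handle the same patient differently and each be following the protocol.

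The all-cause treatment-emergent tables are at stake. At sites that follow 8.2.4 to the letter they would hold some events that are only disease progression, and at other sites they would not. If ECOG is also assessed more often in one arm, a rule that turns each assessed change into an AE can open a gap between arms that has nothing to do with tolerability.

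**Working it through.** The protocol gives no figure to reproduce, so the check sets the passages side by side.

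**Step 1. Is an ECOG decline from melanoma within the progression rule?** Section 8.3.7 counts increased symptoms of the disease as progression. An ECOG decline unequivocally caused by the tumour therefore falls within it and within the exclusion in Appendix B 1. Section 8.2.4 makes the same decline reportable. The conflict is real, but it covers only declines unequivocally due to disease. A decline of uncertain cause is an AE under every section.

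**Step 2. Can a site resolve it from the text?** Sections 8.2.1 (physical examination), 8.2.2 (vital signs), 8.2.5 (laboratory) and 8.2.6.1 (echocardiogram/MUGA) each send the reader to 8.3.5 for AE reporting. Section 8.2.4 does not, and 8.3.5 does not cover ECOG.

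**Step 3. Does the situation arise at planned visits?** Inclusion criterion 11 admits patients with ECOG 0 or 1, so every patient has room to worsen. Progression is the first reason for stopping treatment listed in Section 7.1. Tables 1 and 2 schedule ECOG at treatment discontinuation in both arms.

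**Step 4. Do these reports reach the tables?** A decline first noted at the discontinuation visit, before any subsequent cancer therapy, meets the timing definition in 9.4.3.1 and would be tabulated. Declines with later onset are only listed.

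**Step 5. Is ECOG assessed equally in the two arms within that window?**

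| Scheduled ECOG | Combination (Table 1) | Monotherapy (Table 2) |
|---|---|---|
| Day 1 of each cycle | yes | yes |
| Day 8, Cycles 1, 2 and 3 | yes | no |
| Treatment discontinuation | yes | yes |
| 30 days after last dose | yes | no |

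A combination patient who completes three cycles therefore has 3 + 1 = 4 more scheduled assessments than a monotherapy patient. The 30-day visit has a window of ±3 days and sits at the edge of the treatment-emergent period, so only part of what it finds would count. The combination visits at 60, 90 and 180 days fall outside the period. Both tables allow extra ECOG assessments when clinically indicated, which narrows the difference but does not remove it.

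**Step 6. How large is the effect?** It depends on the rate of progression-related ECOG decline in the window, the share judged significant, and the share of sites that follow 8.2.4 literally. The protocol gives none of these, so no figure can be derived.

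**The case against.** The strongest reply is that AE is a defined term. Section 8.3 sends the reader to Appendix B, which excludes progression, and 8.3.7 is the specific rule on the subject, so a careful site would let those govern 8.2.4. Section 8.3.4 also prefers diagnoses to signs and symptoms, which reduces bare ECOG terms. This limits how many such AEs will be reported. It does not settle the conflict, because 8.2.4 is worded as an obligation with no reference to the definition. Different sites reading it differently is the harm described here.

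Four stronger readings are tempting, and the documents do not support them.

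- *An improvement in ECOG, or a change to grade 5, must be reported as an AE.* Appendix B 1 requires the occurrence to be untoward. Section 8.3.9 has its own rule for deaths, under which death clearly from progression goes on the Statement of Death page and is not an SAE.
- *Progression will be presented as drug toxicity.* The tables affected are all-cause. Section 9.4.3.1 summarises causally related AEs separately, and Appendix B 3 directs that deterioration from lack of effect be rated as having no reasonable possibility of a causal link.
- *The less effective arm will look materially more toxic.* That needs rates of progression and ECOG decline that are not in the protocol. The Synopsis makes safety descriptive, so no planned safety test would be biased.
- *Section 8.3.7 forbids all such reports.* It does not: progression worse than expected for the patient, or thought to be caused by treatment or study procedures, must be reported as an SAE/SUSAR.

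**Conclusion.** The point holds as an inconsistency in AE reporting rules that carries through to the all-cause treatment-emergent summaries. Section 8.2.4 is out of line with the rest of the protocol. Applied literally, it produces AEs that 8.3.7 and Appendix B 1 say should not exist, and the denser ECOG schedule in the combination arm can add them unevenly.

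The conclusion rests on two assumptions: that at least some sites follow 8.2.4 as written, and that no progression filter is applied elsewhere (the protocol states none; the SAP was not available for this check). The size is unknown. Tables of causally related AEs should be largely spared, and the primary ORR analysis is not touched. The point is worth correcting because the stated rule gives a wrong result and the correction is nearly free.

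**What to change.** Reconcile 8.2.4 with 8.3.5, 8.3.7 and Appendix B 1. One possible sentence is: *A clinically significant deterioration in ECOG performance status is reported as an AE unless it is unequivocally due to the disease under study (see Sections 8.3.5 and 8.3.7).* Send sites a short clarification. No information is lost, because Section 9.4.3 already lists ECOG as a safety measure separate from AEs.

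The protocol's summary of changes says that recruitment has ended, so much of the AE data may already be in hand. Keep AEs already reported in the main treatment-emergent tables. Removing them afterwards would depart from the timing-based definition in 9.4.3.1 and would rely on attribution to progression by investigators who know the treatment. At most, add one supplementary summary that identifies or omits AEs whose term is an ECOG change.

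The cost is one sentence, one site clarification and one optional table.
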